**REQUIRED SAMPLE SIZE**

- 30 patients per treatment site for a total of 120 patients.

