### 3.0 SPECIFIC AIMS/OBJECTIVES

**Specific Aim 1:** To estimate the degree of tumor volume, tumor motion and patient anatomy change during treatment with photon beam radiotherapy.

- 1a. To estimate the degree and impact of tumor volume change during the course of definitive photon radiotherapy treatment in lung cancers, head and neck cancers, gastrointestinal cancers (including but not limited to colorectal and rectal cancers) and gynecological cancers.
- 1b. To estimate the degree and impact of tumor motion (anatomic location) change during the course of definitive photon radiotherapy treatment in lung cancers, head and neck cancers, gastrointestinal cancers (including but not limited to colorectal and rectal cancers and gynecological cancers).
- 1c. To estimate the degree and impact of changes in patient anatomy during the course of definitive photon radiotherapy treatment in head and neck and upper gastrointestinal cancers.

Hypothesis: Tumor volume and motion will change over the course of radiation treatment in patients with lung cancers, head and neck cancers, gastrointestinal cancers (including but not limited to colorectal and rectal cancers) and gynecological cancers. The weight loss experienced by patients with upper gastrointestinal and head and neck cancers will have a significant impact on their anatomy. These changes will alter the dose distribution of the photon beam treatment plans, possibly limiting radiation dose delivery to the target volumes and increasing radiation toxicity to surrounding critical structures.

**Specific Aim 2:** To estimate the error if tumor volume, tumor motion and patient anatomy change during treatment with proton beam radiotherapy.

- 2a. To generate simulated proton beam plans using serial CT or MR imaging obtained from either photon or proton beam patients to estimate the dosimetric error if these changes are unaccounted for during proton treatment.

[figure not shown]
Hypothesis: The changes in tumor volume and motion and patient anatomy will have a greater effect on appropriate dose distribution in plans using proton beam therapy compared to photon beam therapy given the need for more accurate target delineation in proton beam therapy.

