## **RADIOTHERAPY PLANNING**

Forward photon and proton beam plans will be generated on the CT simulation data set. These plans will be then be applied to the up to weekly data sets to quantify variance in dose deposition.

**Treatment planning is not routinely changed during the course of radiation therapy. However, if it is found by the treating physician that a significant change has occurred in tumor volume, position or anatomy that render the original plan no longer optimal, then a new treatment plan will be created for the remainder of treatment. Should this occur, the PI will be notified of the treatment changes.**

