## **9.0 STATISTICAL CONSIDERATIONS**

### **9.1 *Background:***

Tumor volume, location and proximity to critical normal organs are determined by CT scans prior to the start of radiation treatment. Radiation dosimetry plans are not re-calibrated during the course of a patient's treatment since it is assumed that changes in these variables are negligible. This hypothesis has rarely been studied in a rigorous manner. Dramatic tumor shrinkage or patient weight loss, may cause the radiation energy beam to over-shoot the treatment target and may also increase the radiation dose to nearby critical normal organs.

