### **9.2 *Study Design:***

This pilot study will determine changes over time in tumor volume and motion and patient anatomy, as well as dose distributions to normal organs. The study will inform medical decision-making about the need for (and timing of) re-calibration of radiation dosimetry plans. Up to weekly CT and/or serial MR scans (minimum of 3) will be employed to measure changes in tumor volume and motion and patient anatomy in patients receiving definitive radiation therapy (with or without concurrent chemotherapy). This study is not designed to evaluate the CT or MR procedure. CT or MR is simply the imaging method used for precise measurement of tumor volume variables. Enrollment will be stratified by disease site: NSCLC, Head & Neck, GI and Gynecologic tumors. The study will enroll 30 patients in each stratum. This study is descriptive and not powered hypothesis testing.

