**9.5 Plans for Data Analysis: To be conducted within each stratum**

1. Tumor Volume: To determine the distributions of volume variables and percent change from baseline. At each scan time point, compute mean, median, range and standard deviation of these variables and plot mean values over time. To compare volume variables at baseline to the values at selected scan time points by paired Wilcoxon signed ranks test.
2. Tumor Motion: At each scan time point, compute mean, median, range and standard deviation of the dose coverage and plot mean values over time. To compare ITV or CTV variables at baseline to the GTV at selected scan time points by paired Wilcoxon signed ranks test.
3. Patient Anatomy: To determine the distribution of patient percent weight loss. At each scan time point, compute mean, median, range and standard deviation of percent weight loss and plot mean values over time.
4. Dose distribution: To determine the distributions of radiation dose to GTV, ITV and critical normal organs. To correlate radiation dose to normal organs with percent weight loss.
5. Conduct exploratory longitudinal analyses to examine changes over time in the 30 patients. Random effects linear regression models will be employed to estimate changes in variables over time clustered by patient. Natural log transformation will be applied prior to modeling.
6. To assess if changes in volume variables are clinically relevant and if so, identify the earliest time point at which re-calibration is warranted. Although it may not be possible to identify a single 're-calibration solution' for all patients in a particular stratum, we will attempt to identify the earliest scan time point at which the majority of patients have clinically important changes in tumor volume or location resulting in over-shoot of the target volume and/or increased dose exposure to normal organs.

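### The re-calibration criterion in 9.5 item 6 omits dose errors that come only from weight loss or anatomy change, so its time point may be late or missing

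*Combined protocol and SAP*

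**What the plan says.** Item 6 of section 9.5 opens with "To assess if changes in volume variables are clinically relevant and if so, identify the earliest time point at which re-calibration is warranted". It then says the analysis will try to find "the earliest scan time point at which the majority of patients have" a qualifying change. The event that qualifies is described as "clinically important changes in tumor volume or location resulting in over-shoot of the target volume and/or increased dose exposure to normal organs". Both sentences name a cause, first the volume variables and then tumor volume or location. Patient anatomy is in neither.

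Elsewhere the cause is drawn more widely:

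- Section 9.1: "Dramatic tumor shrinkage or patient weight loss, may cause the radiation energy beam to over-shoot the treatment target". The same sentence adds higher dose to nearby normal organs.
- Section 3.0, hypothesis under Aim 1: "The weight loss experienced by patients with upper gastrointestinal and head and neck cancers will have a significant impact on their anatomy". It goes on to expect altered dose distributions.
- Section 9.6 lists dramatic weight loss among the key factors in the evaluation.
- Radiotherapy Planning (within 6.5) provides for a new plan if the treating physician finds "a significant change has occurred in tumor volume, position or anatomy that render the original plan no longer optimal".

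Items 3 and 4 of 9.5 summarize percent weight loss at each scan and correlate it with organ dose. Neither feeds the time point in item 6.

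**The concern.** Section 9.2 says the study is meant to inform whether, and when, dosimetry plans need re-calibration. Item 6 is the only analysis that produces a time point. Its event is restricted by cause, and the restriction leaves out a cause that the plan itself names. A patient whose tumor is stable, but whose weight loss raises organ dose under the initial plan, is not an event under the wording of item 6. The omission falls where Aim 1c expects anatomy change to matter: head and neck and upper GI patients.

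The plan also gives no rule for attributing a dose error to tumor or anatomy when both change. Two analysts could therefore count the same patient differently.

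**Working it through.** **Inputs from the plan.** "The study will enroll 30 patients in each stratum" (9.2), and "30 patients per treatment site for a total of 120 patients" (Required Sample Size): 4 × 30 = 120, which reproduces. A majority of 30 is at least 16, if all 30 are scanned at that time point. Section 2.0 puts the share of head and neck patients losing more than 10% of body weight at about 35%, or 0.35 × 30 = 10.5 patients. The plan gives no rate of dose errors from either cause.

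**Direction.** Let A be the patients with a tumor-driven dose event at a scan and B those with a dose event from tumor or anatomy, using the same dose thresholds. A is contained in B at every scan. The first scan at which B exceeds half the stratum therefore cannot come after the first at which A does. Item 6 uses A, so its time point is the same, later or never. This needs no assumed rate.

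**Size (illustrative).** Assume an anatomy-driven share a = 0.35, treating every weight loss above 10% as a dose event, and vary the tumor-driven share p. Combined share:

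- nested groups: max(p, a)
- independent: p + (1 − p) × a
- disjoint: p + a

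For p = 0.40 and independence: 0.40 + 0.60 × 0.35 = 0.61. The chance of a majority at share q is the binomial tail, the sum over k = 16 to 30 of C(30,k) q^k (1 − q)^(30−k).

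| p | Combined share, independent | P(majority), tumor only | Nested | Independent | Disjoint |
|---|---|---|---|---|---|
| 30% | 54.5% | 0.006 | 0.030 | 0.624 | 0.935 |
| 40% | 61% | 0.097 | 0.097 | 0.853 | 0.997 |
| 50% | 67.5% | 0.428 | 0.428 | 0.965 | 1.000 |
| 60% | 74% | 0.825 | 0.825 | 0.996 | 1.000 |
| 70% | 80.5% | 0.983 | 0.983 | 1.000 | not possible (sum 105%) |

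With smaller anatomy shares at p = 40% and independence, the combined share is 46% (a = 10%) or 52% (a = 20%), and P(majority) is 0.266 or 0.516. Under independence the combined share passes 50% when p > 1 − 0.5/(1 − a). That is p > 0.444, 0.375 and 0.231 for a = 10%, 20% and 35%.

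**Timing (illustrative).** Let both shares rise linearly over 7 weekly scans, with anatomy reaching 35% and independent overlap. First week with an expected count above 15 of 30:

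| Final tumor share | Tumor only | Tumor or anatomy |
|---|---|---|
| 40% | never | week 6 |
| 50% | never | week 5 |
| 60% | week 6 | week 5 |
| 70% | week 6 | week 4 |
| 90% | week 4 | week 4 |

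With nested groups the week does not change in any of these rows.

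**The case against.** A reader might infer that dose errors linked to weight loss never count, and that the time point will be too late or missing. The documents do not support that. Aim 1b equates tumor motion with anatomic location, and 6.6 measures it as the percent of the GTV inside the initial ITV. Weight loss that displaces the tumor therefore counts through location, and a patient who also has a tumor-driven event counts anyway. Only anatomy-only errors are lost. They matter only if there are enough of them in a stratum that tumor change has not already carried past a majority.

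A reader might also infer that the conclusion flips from no majority to majority. That depends on choosing tumor shares just below 50% and on independence. The 35% is a weight-loss rate, not a dose-error rate, and section 2.0 does not say in which week the loss occurs. Section 2.0 also cites a 69.5% GTV reduction in head and neck cancer by end of treatment. That is a volume figure, not a dose event, but it makes the stable-tumor patient a less typical example. Even at a combined share of 54.5%, a majority of 30 is missed with probability 1 − 0.624 = 0.376.

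Item 6 sets no minimum size for increased organ dose. A very loose threshold could name a time point early. That is a separate gap and does not reverse the direction shown above, which holds thresholds fixed.

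Finally, item 6 is worded as an attempt, in a study that 9.2 calls descriptive and not powered for hypothesis testing. No error rate or sample size is affected, and the re-planning text already covers anatomy for patient care. All of these points limit the size and weight of the concern. None of them puts anatomy into item 6, and no other section does.

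**Conclusion.** The concern holds in a limited form. Item 6 is narrower than the plan's own account of what causes dose error, and narrower than its own re-planning text, so these passages should be reconciled. The direction is certain for fixed thresholds: same, later or never, not earlier. Whether the time point actually moves is not known. It is most plausible in head and neck and upper GI patients, and upper GI is only part of a mixed GI stratum. It may make no difference where tumor-driven events already reach a majority or overlap with weight loss. The move from 40% to 61% rests on an assumed 35% anatomy-driven share and on independence. With nested groups and a tumor share of 35% or more, there is no change at all. The point is worth correcting because it changes what item 6 can conclude, but it does not undermine the descriptive estimates.

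**What to change.** In both sentences of item 6, replace the reference to volume variables and the reference to tumor volume or location with tumor volume, tumor location or patient anatomy. Count a patient at a scan when the initial plan, applied to that scan, gives over-shoot or increased organ dose, whatever the cause. Report the likely cause descriptively alongside.

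The investigators should set the dose thresholds before analysis. It would be wrong to assume that pass/fail limits are already in the plan. No target-coverage goal is stated, normal-tissue limits appear only in general terms in 6.5 with one lung example in 9.4, and the dose coverage endpoint in 9.4 is geometric.

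Cost: no new scans or measurements, because 6.6 already applies the initial photon and proton plans to each new scan and records dose to GTV, ITV and critical structures. The work is a wording change plus agreement on thresholds for each site. The downside is that cause-specific counts become secondary.

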## **1.0 ABSTRACT**

In recent years, conformal techniques have been developed that allow for precise delivery of radiotherapy to the primary tumor and regional lymphatics while minimizing the dose to normal tissues. Unfortunately, at present, most conformal treatment delivery approaches do not account for changes in tumor volume, tumor motion or changes in patient anatomy during the time course of treatment. Studies have shown that lung, head and neck, and gynecological tumors can change significantly during radiation treatment. Patients can lose significant weight during the radiation treatment, which can alter the patient's body habitus and anatomy. These tumor and anatomical changes can alter radiation dose distribution, resulting in higher radiation doses to normal tissue and lower radiation doses to target volumes. Adapting for changes in tumor motion, tumor volume and patient anatomy can therefore enhance radiation treatment efficacy and widen the therapeutic ratio. Because proton beams require precise target definition, accounting for tumor changes should be critical when using proton beam radiation treatment.

This is a pilot study to quantify the tumor and organ at risk volume and motion path changes that occur during definitive proton beam or photon beam radiotherapy. The patients will undergo CT scans in treatment planning position at the time of CT Simulation. Photon beam treatment plans and proton beam treatment plans will be generated from these images. Based on the location of the primary tumor, patients will undergo either up to weekly 3D or 4D CT and/or a serial of MR scans during treatment. These images will be compared to the initial CT and/or MR scans used for treatment planning and analyzed for changes in tumor volume and tumor anatomic location. At the end of treatment, the /serial images will be compared to the initial treatment planning images to quantify the changes in tumor volume and tumor motion during the course of radiation treatment. Each CT and/or MR scan will also be used to evaluate the changes in dose distribution to the target volumes and normal tissues that occur with the initial photon treatment plan and initial proton treatment plan. The changes in tumor volume, tumor motion and dose distribution during the course of radiation treatment will be analyzed to determine the effect of tumor changes on radiation treatment efficacy.

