In addition to patient anatomy the size of the tumor as well as the anatomic location of the tumor are subject to change during radiation treatment. Fox et al. demonstrated a median GTV reduction of 44.3% at 50Gy in patients with non-small cell lung cancer. Head and neck cancers and cervical cancers are particularly sensitive to radiation effects. Barker et al. demonstrated a 69.5% reduction in GTV volume with a median mass displacement of 3.3mm at the end of radiation treatment in patients with head and neck cancers. Cervical cancers have a median mid treatment regression rate of 69% at 36-45Gy when treated with radiation alone and 79% when treated with concurrent chemoradiation (Nam). The resulting anatomic changes during radiation treatment can have a significant impact on dosimetric distributions, resulting in inadequate dose delivery to the tumor even with 4D CT image guided radiotherapy planning (Britton). Britton et al. evaluated the dosimetric consequences of anatomic changes during conformal photon beam radiotherapy for 10 patients with NSCLC using weekly 4D CT Scans. The authors noted a substantial decrease (-20.5%) in the PTV dose coverage and variable increases in dose to normal tissue structures such as the lung, spinal cord, esophagus and heart. These variations were due to inter and intrafractional variations during treatment.

Ideally, one would account for both inter-and intrafraction variability on a daily basis or after a given number of fractions. (Vanuytsel, Vansteenkiste et al. 2000) This could widen the therapeutic ratio by maximizing dose to the tumor and protecting critical normal structures. Harsolia et al. found that in the treatment of patients with NSCLC, daily respiratory motion and tumor volume correction yielded the maximal decrease in treatment volumes (44% reduction) and the maximal decrease in volume normal lung irradiated (31% reduction) and mean lung dose (31% reduction).

At present, the standard of care is to base the entire course of radiation treatment upon the initial treatment plan, which is derived from the pre-treatment scan. It is easy to envision that treatment re-planning to adjust for anatomical changes may be necessary during the course of radiation treatment. The overall objective of this study is to determine the

**Quantification of Tumor and Organ at Risk (OAR) Volume and Motion Path Changes during Definitive Photon or Proton Beam Radiotherapy**

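### The counting sentence in 9.5 item 6 leaves out reduced target dose or coverage, so the re-calibration time point can be named later than it should be, or not at all

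*Combined protocol and SAP*

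**What the plan says.** Item 6 of 9.5 opens broadly: "To assess if changes in volume variables are clinically relevant and if so, identify the earliest time point at which re-calibration is warranted". It then says what will be sought within each stratum, namely the first scan at which most patients have "clinically important changes in tumor volume or location resulting in over-shoot of the target volume and/or increased dose exposure to normal organs". The same two consequences appear in 9.1, where shrinkage or weight loss "may cause the radiation energy beam to over-shoot the treatment target and may also increase the radiation dose to nearby critical normal organs". Neither place names reduced target dose, and over-shoot is not defined.

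Other parts of the document put target dose beside organ dose:
- The abstract (1.0) describes anatomic change as "resulting in higher radiation doses to normal tissue and lower radiation doses to target volumes".
- The hypothesis under Specific Aim 1 (3.0) speaks of altered dose distribution "possibly limiting radiation dose delivery to the target volumes and increasing radiation toxicity to surrounding critical structures".
- The background (2.0) says of a cited 10-patient photon study with weekly 4D CT: "The authors noted a substantial decrease (-20.5%) in the PTV dose coverage".
- Objective 4 in 9.3 covers dose to the tumor as well as to critical organs.
- 9.4 lists dose coverage as an endpoint, measured as the percent of GTV lying inside the baseline ITV or CTV.
- 6.6 records dose to GTV, ITV and critical structures on each new scan, and 9.5 item 4 describes its distribution.

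**The concern.** Section 9.2 says the study is meant to inform whether and when dosimetry plans should be re-calibrated. Items 1 to 5 of 9.5 yield distributions, paired tests, a correlation and longitudinal models. Only item 6 turns these into a time point. If its count leaves out one of the two harms that the protocol sets out to study, the time point answers a narrower question than the one asked. Under-dose to the target is also the harm most directly tied to tumor control. A stratum could be reported as having no majority, or a late one, while most of its patients had some clinically important dose error.

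**Working it through.** **Plan figures.** 4 strata × 30 patients = 120, which matches the stated total. A strict majority of 30 is 16. The study is described as descriptive, so there is no power calculation to reproduce.

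**Direction (no assumptions about shares).** At a given scan let A be the patients who meet the written criterion, and U those with a clinically important loss of target dose or coverage. With U added to the criterion, the count is |A ∪ U| = |A| + |U not in A|, which is at least |A|. The first scan to reach 16 is then the same or earlier. So the written criterion gives the same or a later scan, or none, and never an earlier one. Only patients in U but not in A make a difference.

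**Size at one scan (illustration; the shares are assumed because the documents give none).** Let a be the share meeting the written criterion and u the further share with under-dose only. The chance of a majority is P(X ≥ 16) for X ~ Binomial(30, p), with p = a as written and p = a + u with under-dose counted.
- a = 0.40, u = 0.10: 0.097 becomes 0.428 (expected count 12 becomes 15).
- a = 0.40, u = 0.20: 0.097 becomes 0.825 (12 becomes 18).
- a = 0.50, u = 0.10: 0.428 becomes 0.825 (15 becomes 18).
- a = 0.40, u = 0 (full overlap): 0.097 stays 0.097.

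**Timing (illustration).** Assume seven weekly scans and shares rising linearly, so the expected count in week w is 30 × (week-7 share) × w/7. Take the first week with an expected count of at least 16.

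| Written criterion, week-7 share | Under-dose only, week-7 share | Week as written | Week with under-dose counted |
|---|---|---|---|
| 40% | 10% | none | none |
| 40% | 20% | none | 7 |
| 60% | 10% | 7 | 6 |
| 60% | 20% | 7 | 5 |
| 80% | 10% | 5 | 5 |
| 80% | 20% | 5 | 4 |
| 40%, 60% or 80% | 0% | none, 7 or 5 | unchanged |

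Worked row (60% and 10%). As written: 30 × 0.60 × 6/7 = 15.4 in week 6 and 18.0 in week 7. With under-dose counted: 30 × 0.70 × 5/7 = 15.0 in week 5 and 30 × 0.70 × 6/7 = 18.0 in week 6.

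Across these assumed shares the shift runs from nothing to two weeks, or from no time point to week 7.

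**The case against.** Several points on the other side stand.

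- A reader might infer that under-dosed patients never count. The text does not support that. The two consequences are joined by and/or, so an under-dosed patient who also has over-shoot or a higher organ dose is already in. Overlap is plausible: the cited photon study reports variable increases in normal-tissue dose alongside the coverage loss.
- A reader might infer that the time point will be late. The documents support only that it can be, since they give no share with under-dose only.
- A reader might treat a tumor that has moved outside the baseline ITV as under-dosed. That does not follow, because 9.4 places the CTV and PTV beyond the ITV. For an assumed spherical GTV of 2 cm radius with a 5 mm ITV margin, a 1.0 cm shift leaves 11.5% outside the ITV, but 0% outside a volume with 5 mm more margin. The one displacement figure in 2.0, a median of 3.3 mm in head and neck cancer, leaves nothing outside even the ITV in this model (2.0 + 0.33 = 2.33 cm, inside 2.5 cm).
- Section 2.0 also cites an 8-patient proton study that found CTV coverage adequate when 4D planning accounts for motion, with high dose spilling into normal tissue. That fits the two consequences in item 6.
- Target loss is not hidden. Items 2 and 4 of 9.5 report coverage and target dose within each stratum.
- Item 6 is worded as an attempt, sets no threshold for clinical importance, and governs no enrolled patient's care. The planning section leaves re-planning to the treating physician.

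Two replies do not remove the point. The broad opening of item 6 is narrowed by the sentence that defines the count. Over-shoot might be stretched to cover a beam that misses a displaced target, but 9.1 ties it to shrinkage and weight loss, and a beam that stops short is not plainly included.

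**Conclusion.** The omission is real and conflicts with the document's own hypothesis, objective 4 and coverage endpoint. Followed as written, item 6 does not count patients whose only dose consequence is target under-dose. The resulting time point is the same or later, or absent, and never earlier. That much rests on the wording and on the count being taken over the same patients.

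The size is undetermined. It depends on the share with under-dose only and is zero with full overlap. The probabilities and weeks above are illustrations, not estimates for this trial. Because item 6 is a descriptive attempt and target dose is reported elsewhere in 9.5, this is a should-fix. It does not invalidate the analysis.

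**What to change.** In 9.5 item 6, ahead of the two consequences already listed, add *reduced dose to or coverage of the target volumes*, keeping the and/or. State what over-shoot means, including whether it covers a beam that misses a displaced target. Say whether the new component uses the geometric coverage endpoint in 9.4, the GTV and ITV doses recorded under 6.6, or both. At each scan and in each stratum, tabulate the number of patients meeting each component separately and combined, so that the overlap can be seen. The sponsor should set, before analysis, what counts as clinically important for each component; no threshold is proposed here.

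The cost is one clause, one definition and one further table from data already planned. The downside is that the named time point may be earlier.
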